### 4.2. Secondary Hypotheses

- 1. Subjects wearing the JJVCI Investigational contact lenses on a daily wear basis will have patient reported handling at the 2-Week Follow Up visit that is non-inferior to that of subjects wearing predicate device on a daily wear basis. A non-inferiority margin of -5 CLUE points will be used.
- 2. Subjects wearing the JJVCI Investigational contact lenses on a daily wear basis will have patient reported vision at the 2-Week Follow Up visit that is non-inferior to that of

subjects wearing predicate device on a daily wear basis. A non-inferiority margin of -5 CLUE points will be used.

## 4.3. Other Hypotheses

Not applicable.

## 5. ANALYSIS SETS

## 5.1. All Enrolled

The All Enrolled population will include all participants who sign an informed consent.

## 5.2. Intent-to-Treat (ITT)

All randomized subjects regardless of actual treatment and subsequent withdrawal from study or deviation from protocol. At least one observation should be recorded.

Safety variables will be summarized on both safety and PP populations whereas efficacy variables will be summarized on the per-protocol and Intent-to-Treat population.

## 5.3. Safety Population

All subjects who were administered any test article excluding subjects who drop out prior to administering any test article. At least one observation should be recorded.

## 5.4. Per-Protocol (PP)

Per Protocol Analysis set will be the primary analysis population. It will include all subjects who have successfully completed all visits and did not substantially deviate from the protocol as determined by the trial cohort review committee prior to database hard lock. Justification of excluding subjects with protocol deviations in the per-protocol population set will be documented in a memo to file.

## 6. DEFINITIONS AND DERIVED VARIABLES

## 6.1. Age

Age will be calculated using the Date of Birth (DOB) and the date of the consenting the subject and presented as age at last birthday as an integer.

Age = Integer part of [(Date of Baseline visit – Date of Birth) / 365.25]

# 6.2. Average daily wear time (in Hours)

Average daily wear time will be calculated as the number of hours between subjects reported time of insertion and time of removal of the study lenses, on an average day, at 2-Week Follow-up evaluation.

#### 6.3. **Iris Category**

Iris color will be categorized into either dark or light based on the subjects' hue and lightness of their iris using Johnson & Johnson's Iris Color Scale. If hue is brown or lightness is dark then the subject will be classified as having a dark iris, if hue is light then the subject will be classified as having a light iris. If lightness is medium and hue is green, blue or grey then the subject will be classified as having a light iris; otherwise subjects will be classified as having a dark iris.

#### 6.4. Visit Windows

Table 4: Visit Window information			
Scheduled Visit	Time Interval	Time Interval	Target Time
Number	(label on output)	(Day) a	Point
1	Baseline	1	1
1	Fitting	1	1
2	2-Week Follow-up	13 to 15	14
a The first treatment day is Day 1			

The first treatment day is Day 1.

#### 6.5. **Definition of Subgroups**

There is no planned subgroup analysis for this study.

#### 7. **GENERAL STATISTICAL CONSIDERATIONS**

#### 7.1. **Statistical Software**

All data summaries and statistical analyses will be performed using the SAS software Version 9.4 or higher (SAS Institute, Cary, NC).

#### 7.2. **Summary Statistics**

Throughout the analysis of data, the results for each subject/eye will be used when available for summarization and statistical analysis. Unscheduled visits will be summarized separately and will be excluded from the efficacy statistical analysis but will be included in the analysis of safety endpoints (slit lamp findings and lens fitting).

Summary tables (descriptive statistics and/or frequency tables) will be provided for all baseline variables, efficacy variables and safety variables as appropriate. Continuous variables will be summarized with descriptive statistics (n, mean, standard deviation [SD], median, minimum and maximum). Frequency count and percentage of subjects or eyes within each category will be provided for categorical data.

Safety variables will be summarized on both safety and PP populations whereas efficacy variables will be summarized on the PP and ITT populations.

#### 7.3. **Reporting Numerical Values**

Means, medians and confidence/credible intervals will be reported to one decimal place greater than the original data. The standard deviation will be reported to two decimal places greater than CR-6305, Statistical Analysis Plan Version 1.0 Page 13 of 33

13

the original data. Minimum and maximum will use the same number of decimal places as the original data. P-values greater or equal than 0.0001 will be reported to 4 decimal places; p-values less than 0.0001 will be reported as "<0.0001". All percentages will be reported to one decimal place.

# 7.4. Sample Size Justification

This study was designed and powered to show non-inferiority of the Test lens compared to the Control lens with respect to logMAR Visual Acuity, Slit Lamp Findings (Grade 3 or higher) and CLUE comfort. It was assumed there was no difference between the Test and Control lens with respect to slit lamp findings and a 1 letter difference (0.02) between the Test and Control lenses with respect to visual acuity logMAR. Based on data from 3 historical studies, it was assumed there was a 2-point difference between the Test and Control lenses with respect to CLUE comfort based on the summary statistics from the first period of the historical studies.

In addition to the endpoints mentioned above this study was also powered to demonstrate noninferiority of the Test lens relative to the Control lens with respect to vision satisfaction in bright lighting and the proportion of eyes with acceptable fitting while the Test lens is significantly superior to 90%.

Unless otherwise specified, the sample size was calculated to achieve a minimum statistical power of 80% and a type I error of 5%.

A total of 5 historical studies were utilized in the sample size calculation. Table 5 displays the studies, their corresponding study design and the number of subjects enrolled and completed perprotocol.

			No.	No. Completed
Study	Study Design	Endpoints Collected	Enrolled	Per-Protocol
	2X3 Crossover	CLUE, SLF Lens Fit	135	132
	2X3 Crossover	CLUE, Visual Acuity (logMAR), SLF, Lens Fit	133	121
	2X3 Crossover	CLUE, SLF Lens Fit	92	78
	Single-Arm	SLF, Lens Fit	54	48
	Single-Arm	SLF, Lens Fit	56	41

Table 5: Historical Studies Included in Sample Size Calculation

CLUE Domain [Mean(SD)  ]	Test	Control

Comfort	66.66 (21.066)	63.90 (24.197)
Handling	69.32 (18.454)	71.11 (20.429)
Overall Quality of Vision	64.49 (17.221)	64.44 (23.351)

SD = Standard Deviation

Table 7: Descriptive Summary of Visual Acuity (logMAR) - 2-Week Follow-up Evaluation-Period 1 Only

Visual Acuity High Illumination High Contrast	Test	Control
[Mean(SD)  ]	-0.088 (0.0862)	-0.0622 (0.0740)

SD = Standard Deviation

#### Table 8: Descriptive Summary of Mechanical Lens Fitting Pooled Across all Historical Studies

Any Unacceptable Lens Fit  [n(%)]	Test n (%)	Control n (%)
Fitting Evaluation	0(0.0)	0 (0.0)
2-Week Follow-up	0 (0.0)	0 (0.0)

The percent of any unacceptable fit is calculated using Total Unique eyes as a denominator

#### Table 9: Descriptive Summary of Slit Lamp Findings Pooled Across all Historical Studies

SLF Grade 2	Test n (%)	Control n (%)
Corneal Edema	0 (0.0)	0 (0.0)
Conjunctival Injection	59 (6.86)	59 (21.85)
Tarsal Abnormalities	51 (5.93)	24 (8.89)
Corneal Neovascularization	3 (0.35)	0 (0.0)
Corneal Staining	3 (0.35)	0 (0.0)
Other Findings	0 (0.0)	0 (0.0)
Total Eyes (N)	860	270
	·	
Any SLF Grade 2 	116 (13.48)	83 (33.74)
Any SLF Grade 3+	0 (0.0)	0 (0.0)
Total Unique Eyes	860	270
Total Unique Subjects	430	135

%= nx100/N; SD=Standard Deviation

All SLF reported for this study are combined for the purposes of summarizing

 The percent (%) of Any Grade 2 is calculated using the Total Unique Eyes as the denominator

Table 10: Descriptive Summary of Individual Ite	em from – 2-Weel	- 2-Week Follow-up	
Questionnaire Item/ Response	Test	Control	
Vision Satisfaction in Bright Light [n(%)]			
Strongly Agree	72 (29.75)	51 (21.07)	
Agree	129 (53.31)	130 (53.72)	
Neither Agree Nor Disagree	24 (9.92)	21 (8.68)	
Disagree	17 (7.02)	33 (13.64)	
Strongly Disagree	0 (0.0)	7 (2.89)	

#### **CLUE Comfort Scores**

With respect to CLUE comfort, based on historical data from Period 1, a mean difference of 2 points was assumed and a standard deviation of 21, an additive equivalence test in PROC Power for two sample means was used to Test for non-inferiority. A non-inferiority margin of -5 points was used since this is considered to be no more than a 10% shift in the distribution of CLUE scores.

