14.2. Sample Size Justification

This study was designed and powered to show non-inferiority of the Test lens compared to the Control lens with respect to logMAR Visual Acuity, Slit Lamp Findings (Grade 3 or higher) and CLUE comfort. It was assumed there was no difference between the Test and Control lens with respect to slit lamp findings and a 1 letter difference (0.02) between the Test and Control lenses with respect to visual acuity logMAR. Based on data from 3 historical studies, it was assumed there was a 2-point difference between the Test and Control lenses with respect to CLUE comfort based on the summary statistics from the first period of the historical studies.

In addition to the endpoints mentioned above, this study was also powered to demonstrate non-inferiority of the Test lens relative to the Control lens with respect to vision satisfaction in bright lighting and the proportion of eyes with acceptable fitting while the Test lens is significantly superior to 90%.

Unless otherwise specified, the sample size was calculated to achieve a statistical power of at least 80% and a type I error of 5%.

A total of 5 historical studies were utilized in the sample size calculation. Table 6 displays the studies, their corresponding study design and the number of subjects enrolled and completed perprotocol.

Study	Study Design	Endpoints Collected	No. Enrolled	No. Completed Per-Protocol
	2X3 Crossover	CLUE, SLF Lens Fit	135	132
	2X3 Crossover	CLUE, Visual Acuity (logMAR), SLF, Lens Fit	133	121
	2X3 Crossover	CLUE, SLF Lens Fit	92	78
	Single-Arm	SLF, Lens Fit	54	48
	Single-Arm	SLF, Lens Fit	56	41

Table 6: Historical Studies Included in Sample Size Calculation

 Table 7: Descriptive Summary of CLUE Scores by Domain Pooled Across Historical Studies

 - 2-Week Follow-up Evaluation Period 1 only

CLUE Domain		· · · · · · · · · · · · · · · · · · ·
[Mean(SD) ¹]	Test	Control
Comfort	66.66 (21.066)	63.90 (24.197)
Handling	69.32 (18.454)	71.11 (20.429)

Overall Quality of Vision	64.49 (17.221)	64.44 (23.351)

 1 SD = Standard Deviation

Table 8: Descriptive Summary of Visual Acuity (logMAR) - 2-Week Follow-up	
Evaluation-Period 1 only	

Visual Acuity High Illumination High Contrast	Test	Control
[Mean(SD) ¹]	-0.088 (0.0.0862)	-0.0622 (0.0740)

 1 SD = Standard Deviation

Table 9: Descriptive Summary of Mechanical Lens Fitting Pooled Across all Historical Studies

Any Unacceptable Lens Fit ¹ [n(%)]	Test n (%)	Control n (%)
Fitting Evaluation	0(0.0)	0 (0.0)

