$$\sum_{Visual\ Acuity} \begin{pmatrix} 0.004047 & 0.002894 \\ 0.002894 & 0.004737 \end{pmatrix}$$

Slit Lamp Findings

There were no Grade 3 or higher SLFs observed in any of the historical studies. Assuming no difference between study lenses and a correlation 0.70 between left and right eyes within the same subject (intra-subject correlation), a reference rate of no more than 5% was assumed (worse-case scenario) with a non-inferiority odds ratio margin of 2. A total of 2000 replicating trials were simulated, each replicated sample was analyzed using a generalized estimating equation (GEE)

model with a binary distribution and the logit as the link function. Each model included lens type as the only fixed, eye was included as a random effect. The Odds ratio and corresponding 95% confidence interval was used estimate differences between the Test and Control lenses. The upper limit of each 95% confidence interval was compared to 2; if the upper limit was below 2 then NI=1; otherwise NI=0. Statistical power was calculated as the average NI. A sample size of 224 (112 per arm) was chosen to achieve a minimum statistical power of 80%.

Using a reference rate for the control of 5% and no more than a 5% difference between the Test and Control lenses translate to an odds ratio margin of 2. A reference rate of 5% was used as the worst-case scenario.

Individual Questionnaire Items

Vision satisfaction in bright lighting sample size estimates were calculated using historical data from CR-5960.⁷ One-thousand boot strap samples were simulated based on the historical data. For each replicated sample a generalized linear mixed model was used with a multinomial distribution and the cumulative logit as the link function. Lens type was included in the model as the only fixed effect.

Using a reference rate of 50% for the Control lens and assuming no difference between the Test and Control a 10% difference translate to a cumulative odds ratio margin of 0.67. the reference rate of 0.50 was used as the worst-case scenario.

Endpoint	Number per Subjects to Complete	Power
Distance Monocular Visual Acuity (logMAR)	30	86%
SLFs (Grade 3 or Higher)	224	80%
Acceptable lens Fit (Test Lens Only)	100	82%
CLUE Comfort	224	87%
Vision Satisfaction in Bright Lighting	40	87%

Table 12: Sample Size Estimates and Power Calculations for Primary Endpoints

Endpoint	Number per Subjects to Complete	Power
CLUE Handling	224	63%
CLUE Overall Quality of Vision	224	71%

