## 4. STATISTICAL HYPOTHESES FOR STUDY OBJECTIVES

#### 4.1. Primary Hypotheses

All the primary hypotheses must be met in order to satisfy the primary objective of this study.

- 1. Subjects wearing the JJVCI Investigational contact lenses on a daily wear basis will have patient reported comfort at the 2-Week Follow Up visit that is non-inferior to that of subjects wearing predicate device on a daily wear basis. A non-inferiority margin of -5 CLUE points will be used.
- 2. Subjects wearing the JJVC Investigational contact lenses on a daily wear basis will report distance monocular visual acuity (logMAR: bright room luminance / high contrast charts) at the 2-Week Follow Up visit that is non-inferior to that of subjects wearing predicate device on a daily wear basis. A non-inferiority margin of 0.05 LogMAR will be used.
- 3. Subjects wearing the JJVCI Investigational contact lenses on a daily wear basis will have patient reported outcome (Agree and Strongly Agree) on the Quality of Vision in Bright Light at the 2-Week Follow Up visit that is non-inferior to that of subjects wearing predicate device on a daily wear basis. A non-inferiority margin of 10% will be used.
- 4. Subjects wearing the JJVC Investigational contact lenses on a daily wear basis will have a percentage of any grade 3 or higher slit lamp findings at all visits (scheduled and unscheduled) that is non-inferior to that of subjects wearing predicate device on a daily wear basis. A non-inferiority margin of 5% will be used.
- 5. At least 90% of eyes wearing the JJVC Investigational contact lenses on a daily wear basis will have acceptable fits across the fitting and follow-up visits.

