#### Vision Satisfaction

Vision satisfaction in bright lighting sample size estimate was calculated using historical data One-thousand boot strap samples were simulated based on the historical data. For each replicated sample a generalized linear mixed model was used with a multinomial distribution and the cumulative logit as the link function. Lens wear was included in the model as the only fixed effects.

Using a reference rate of 0.50 for the Control lens and assuming no difference between the Test and Control a 10% difference translate to a cumulative odds ratio margin of 0.67. the reference rate of 0.50 was used since this is considered to be the worst-case scenario.

	Number per Subjects to	
Endpoint	Complete	Power
Distance Monocular Visual Acuity (logMAR)	30	86%
SLFs (Grade 3 or Higher)	224	80%
Acceptable lens Fit	100	82%
CLUE Comfort	224	87%
Vision Satisfaction in Bright Lighting	40	87%

Table 11: Sample Size Estimates and Power	Calculations for Primary Endpoints
---	------------------------------------

Table12: Sample Size Estimates and Power Calculations for Secondary Endpoints

Endpoint	Number per Subjects to Complete	Power
CLUE Handling	224	63%
CLUE Overall Quality of Vision	224	71%

As indicated in Table 10 and 11 above, the sample size chosen for this study was primary driven by Slit Lamp Findings (Grade 3 or higher) and CLUE Comfort. The plan is to enroll 236 eligible subjects (118 subject per arm) with a target of 112 subjects to complete each arm in the study. During the enrollment period, the subject drop-out rate with be closely monitored, if an unexpectedly high dropout rate is observed, then the targeted total enrollment number maybe be increased accordingly to ensure that a minimum of 224 subjects complete the study.

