### **CLUE Overall Comfort**

CLUE Comfort scores will be analyzed using a Bayesian normal random-effects model to compare the Test and Control lenses at the 2-week follow-up evaluation. The regression model will include baseline CLUE comfort scores and lens type as fixed effects. Clinical site will be included as random effects. Other subject characteristics such as age, gender, race and iris category will be included as fixed covariates when appropriate.

The Model:

Let  $y_{ijk}$  denote the CLUE Comfort score for the  $k^{th}$  subject at the  $j^{th}$  site, assigned to the  $i^{th}$  lens. The likelihood for  $y_{ijk}$  is constructed as follows:

$$y_{ijk} \sim N(\mu_{ijk}, \sigma_{ijkl}^2)$$

Where

$$\mu_{ijkl} = \mu_0 + \beta_1 Lens_i + \beta_2 baseline + \gamma_j$$

In this model, we define  $Lens_i=0$  for the Control lens and  $Lens_i=1$  for the Test lens. So  $\beta_1$  stands for the difference between the Test and Control lens with respect to CLUE comfort; A positive  $\beta_1$  indicates the Test performed better than the Control.

We assume random site effects are independent and identically distributed (i.i.d) as  $\gamma_j \sim N(0, \sigma_{sits}^2)$  for site for j=1, 2, 3, 4, 5, 6 (site).

For the  $\beta$  coefficients, independent non-informative priors N(0, 1000) will be used. For the variance of random effect of  $\sigma_{site}^2$  an independent non-informative conjugate prior, inverse-gamma(0.001, 0.001) will be used. Starting values for the mean and variance of CLUE scores will be 60 and 400 (since standard deviation of CLUE is normalized to be 20), respectively. The Metropolis sampler algorithm as implemented in the SAS/STAT MCMC 14.2 procedure will be used to estimate the posterior distribution of the unknown parameters. Inferences will be made based on the 95% posterior credible intervals for relevant parameters.

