#### Hypothesis Testing

The null and alternative hypotheses for CLUE comfort non-inferiority of the Test lens relative to the Control lens are as follows:

$$\begin{array}{l} H_0: \ \beta_1 \le -5 \\ H_A: \ \beta_1 > -5 \end{array}$$

Non-inferiority will be declared if the lower bound of the 2-sided 95% credible interval of the difference between the Test lens and the Control lens is greater than -5, i.e.,  $P(\beta_1 > -5) \ge 0.975$ .

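### The 87% power stated for CLUE comfort does not follow from its printed inputs: they give 80% at one-sided 5% and, before baseline adjustment, 70% under the plan's one-sided 2.5% rule

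*SAP*

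**What the plan says.** Protocol 14.2 and SAP 7.4 size comfort in the same words: "a mean difference of 2 points was assumed and a standard deviation of 21, an additive equivalence test in PROC Power", applied to two sample means with a non-inferiority margin of -5 points. No covariate is mentioned, and the one-sided level is not given. The general statement in Protocol 14.2 is that, unless otherwise specified, "the sample size was calculated to achieve a statistical power of at least 80% and a type I error of 5" per cent. SAP 7.4 says the same: "the sample size was calculated to achieve a minimum statistical power of 80% and a type I error of 5" per cent.

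The results table, "Table 12: Sample Size Estimates and Power Calculations for Primary Endpoints", and its counterpart, SAP Table 11, give 224 subjects and 87% for comfort. The SAP adds that "the sample size chosen for this study was primary driven by Slit Lamp Findings (Grade 3 or higher) and CLUE Comfort".

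The 2 points are attributed to Period 1 of the historical studies. The historical CLUE summary (Protocol Table 7, repeated in SAP 7.4) shows comfort of 66.66 (SD 21.066) for Test and 63.90 (SD 24.197) for Control.

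For the analysis, SAP 10.1 states: "Non-inferiority will be declared if the lower bound of the 2-sided 95% credible interval" of the difference exceeds -5, written as P(beta1 > -5) >= 0.975. Protocol 14.5 has the same rule. On the model: "The regression model will include baseline CLUE comfort scores and lens type as fixed effects".

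**The concern.** Two things do not fit. The printed inputs do not lead to the printed power. And the level at which 80% can be reached from those inputs is looser than the level at which the endpoint will be judged.

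This matters because comfort is one of two endpoints said to set the sample size, and SAP 4.1 makes success conjunctive: "All the primary hypotheses must be met in order to satisfy the primary objective of this study". A shortfall on comfort alone therefore lowers the chance that the study meets its objective. The reader is told 87%, and at least 80% in general. Under the actual rule both statements depend on a correlation that neither document reports.

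**Working it through.** **Inputs.** Difference 2 in favour of Test, SD 21 and margin -5 (SAP 7.4, Protocol 14.2). 112 completers per arm (SAP Table 2, Protocol Table 2). Stated power 87%. The sign of the difference is taken from the historical means.

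**Formula.** SE = SD × sqrt(2/n). Noncentrality = (difference + 5)/SE. Power is the probability that a noncentral t with 2n - 2 degrees of freedom exceeds the one-sided critical value.

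**Step 1: try to reproduce 87%.** SE = 21 × sqrt(2/112) = 2.806. With 2 points the distance to the margin is 7 and the noncentrality is 7/2.806 = 2.494. With the unrounded historical difference, 66.66 - 63.90 = 2.76, the distance is 7.76 and the noncentrality is 2.765. On 222 degrees of freedom the critical values are 1.652 (one-sided 5%) and 1.971 (one-sided 2.5%).

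| Difference | One-sided 5% | One-sided 2.5% (actual rule) |
|---|---|---|
| 2 (stated) | 80.0% | 70.0% |
| 2.76 (historical, unrounded) | 86.7% | 78.6% |

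The stated inputs give 87% at neither level. With SD 21, a result that rounds to 87% needs a difference of 2.73 to 2.87 at one-sided 5%, or 3.63 to 3.77 at one-sided 2.5%. Other readings also fail: equivalence bounds of -5 and +5 give about 8% at 5%, and 224 per arm gives 97% and 94%.

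**Step 2: sensitivity under the actual rule, difference 2, unadjusted.**
- SD 20 (the CLUE population SD): 74%.
- SD 22.7, the root mean square of 21.066 and 24.197: 63%. Equal weighting is an assumption, because Period 1 arm sizes are not given.
- No dropout: 71% with 116 per arm and 72% with 118 per arm.

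**Step 3: baseline adjustment.** Replace SD by SD × sqrt(1 - r²) and use 221 degrees of freedom at one-sided 2.5%. The correlation r is an assumption throughout.

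| r | Difference 2 | Difference 2.76 |
|---|---|---|
| 0 | 70% | 79% |
| 0.2 | 72% | 80% |
| 0.4 | 77% | 85% |
| 0.5 | 82% | 89% |
| 0.6 | 87% | 93% |

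80% is reached at r of about 0.46 with 2 points, and about 0.18 with 2.76.

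**Step 4: the secondary CLUE rows, same method.**
- Vision is stated as 71%. The historical difference of 64.49 - 64.44 = 0.05 with the Test SD of 17.221 gives 70.6% at one-sided 5%, and 59% at one-sided 2.5%.
- Handling is stated as 63%. At one-sided 5% with zero difference, the two arm SDs (20.429 and 18.454) give 57% to 65% and their equal-weight pooled value (19.47) gives 61%; none is 63%. At one-sided 2.5%, zero difference gives 45% to 52% (Control to Test SD). The table difference of 69.32 - 71.11 = -1.79 gives 23% to 25% (pooled to Test SD).

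**The case against.** The best defence has four parts.

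**The stated standard is met.** The plan promises at least 80% at a 5% type I error, and at one-sided 5% the printed inputs give 80.0%. On that reading 224 is justified and only the 87% cell is wrong. Slit lamp findings were sized separately at 224, so correcting comfort alone would not move the total. All of this stands as far as the total is concerned. It does not rescue the 87%, and the endpoint is not judged at one-sided 5%: SAP 10.1 requires 0.975, and SAP 7.5 makes tests 2-sided by default.

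**The 70% belongs to an unadjusted test that will not be run.** The planned model includes baseline comfort, so the true power under the rule is undetermined and may exceed 80%. This is right, and it is why 70% is quoted only as the unadjusted figure. But the sizing describes a plain two-sample comparison, and no correlation is given to support a higher number.

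**2.76 points is not the only route to 87%.** With 2 points at one-sided 5%, an SD of about 18.7 to 19.0 also rounds to 87%. That stands: the source cannot be settled from the documents. The 2 and the 2.76 still need reconciling, because the text attributes the 2 points to summary statistics that show 2.76, which does not round to 2.

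**The secondary rows are openly under 80% and print no inputs of their own.** This is fair, and their recomputed values depend on the inputs chosen. For example, zero difference with SD 17 also gives 71% for vision at one-sided 5%, and an SD near 18.85 gives 63% for handling. They are follow-on corrections, not the main point.

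**Conclusion.** The concern holds. The printed comfort inputs give 80.0% at one-sided 5% and 70.0% at the one-sided 2.5% rule without baseline adjustment, 7 and 17 percentage points below the stated 87%. Even the more favourable 2.76 points gives 78.6% under the rule, just below the plan's minimum.

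These figures assume 112 completers per arm, a common SD of 21 and a t-test approximation to the Bayesian rule; the N(0, 1000) prior has negligible influence at an SE of 2.8. With baseline adjustment the power could lie anywhere from 70% to 87% with 2 points, for assumed correlations from 0 to 0.6. So the stated power and its justification are wrong as written, but the sample size is not shown to be inadequate.

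**What to change.** In Protocol Table 12 and SAP Table 11:

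1. Recompute the comfort row at one-sided 2.5%, and state that level in the sizing text.
2. State the inputs actually used, and reconcile the 2-point difference with the 2.76 points in the historical table.
3. Then do one of two things. Either report about 70% (2 points, SD 21, unadjusted) and amend the 80% statement for comfort, or give the residual SD and the documented baseline/follow-up correlation that support a higher figure.
4. Recompute vision and handling at the same level and print their inputs. Vision becomes about 59% with its apparent inputs. The origin of handling's 63% has to be stated, because it cannot be determined from the documents.

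The cost is a table and wording correction, or one added sentence on the correlation. The margin, model, decision rule and enrolment do not change. The only drawback is that the stated power may be less favourable.

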2-Week Follow-up	0 (0.0)	0 (0.0)

¹The percent of any unacceptable fit is calculated using Total Unique eyes as a denominator

Table 10: Descriptive Summary of Slit Lamp Findings Pooled Across all Historical Studies

SLF Grade 2	Test n (%)	Control n (%)
Corneal Edema	0 (0.0)	0 (0.0)
Conjunctival Injection	59 (6.86)	59 (21.85)
Tarsal Abnormalities	51 (5.93)	24 (8.89)
Corneal Neovascularization	3 (0.35)	0 (0.0)
Corneal Staining	3 (0.35)	0 (0.0)
Other Findings	0 (0.0)	0 (0.0)
Total Eyes (N)	860	270
Any SLF Grade 2 ²	116 (13.48)	83 (33.74)
Any SLF Grade 3+	0 (0.0)	0 (0.0)
Total Unique Eyes	860	270
Total Unique Subjects	430	135

%= nx100/N; SD=Standard Deviation

¹All SLF reported for this study are combined for the purposes of summarizing
² The percent (%) of Any Grade 2 is calculated using the Total Unique Eyes as the denominator

Table 11: Descriptive Summary of Individual Item from - 2-Week Follow-up				
Questionnaire Item/ Response	Test	Control		
Vision Satisfaction in Bright Light [n(%)]				
Strongly Agree	72 (29.75)	51 (21.07)		
Agree	129 (53.31)	130 (53.72)		
Neither Agree Nor Disagree	24 (9.92)	21 (8.68)		
Disagree	17 (7.02)	33 (13.64)		
Strongly Disagree	0 (0.0)	7 (2.89)		

CLUE Comfort Scores

With respect to CLUE comfort, based on historical data from Period 1, a mean difference of 2 points was assumed and a standard deviation of 21, an additive equivalence test in PROC Power for two sample means was used to Test for non-inferiority. A non-inferiority margin of -5 points was used since this is considered to be no more than a 10% shift in the distribution of CLUE scores.

Mechanical Lens Fit (Test Lens)

The estimated sample size to test the primary hypothesis (H0 PT \leq P0, H1: PT > P0) is 100. The sample size was calculated using PROC POWER for one sample proportion using an exact Test of a Binomial Proportion.

Visual Performance (logMAR)

Sample size calculation for visual performance (logMAR) was carried out using an approximation of the power of an F-test derived from the non-centrality parameter calculated form the observed F statistic of a linear model.⁸

Model details:

visual performance was analyzed using a linear mixed model. Lens type was included as the only fixed effect. A compound symmetric (CS) covariance matrix was used to model the correlation between measurements on the same subject across study periods. Below is the variance-covariance matrix used in the visual performance model.

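### CLUE comfort is sized with SD 21, which matches only the historical Test arm; the two-arm Period 1 value is about 22.7 and lowers power by about 5 to 7 points

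*SAP*

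**What the plan says.** SAP 7.4 (CLUE Comfort Scores) and Protocol 14.2 describe the same calculation. The protocol attributes the inputs to earlier data: "based on historical data from Period 1, a mean difference of 2 points was assumed and a standard deviation of 21". The SAP names the method: "a mean difference of 2 points was assumed and a standard deviation of 21, an additive equivalence test in PROC Power for two sample means". On the margin it says: "A non-inferiority margin of -5 points was used since this is considered to be no more than a 10% shift". Neither text mentions baseline adjustment or a correlation.

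The Period 1 summary is printed in both documents (Protocol Table 7 and the historical CLUE table in SAP 7.4). For comfort it gives Test 66.66 (SD 21.066) and Control 63.90 (SD 24.197), an observed difference of 2.76.

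The plan is sized "with a target of 112 subjects to complete each arm in the study". The comfort row of the power table (SAP Table 11, Protocol Table 12) reads "CLUE Comfort 224 87" per cent. On the general target, SAP 7.4 says that "the sample size was calculated to achieve a minimum statistical power of 80% and a type I error of 5" per cent; it does not say whether that level is one-sided or two-sided for comfort.

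The decision rule (SAP 10.1, Protocol 14.5) requires the lower bound of a 2-sided 95% credible interval to exceed -5, which corresponds to one-sided 2.5%. The analysis model includes baseline comfort as a covariate.

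**The concern.** The variance of a Test-minus-Control difference contains both arms. The plan cites Period 1 as its source, and that source shows a clearly larger SD for Control. A common SD of 21 leaves the larger SD out, and no reason is given. It understates the variance by about 14%: 21² = 441 against 514.6 when both arms are used.

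Comfort is one of five primary hypotheses that must all be met (SAP 4.1), and SAP 7.4 names it with slit lamp findings as a driver of the sample size. A comfort power that is too favourable therefore makes the chance of meeting the whole primary objective look better than the plan's own data support.

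**Working it through.** **Inputs.** Difference 2, SD 21 and margin -5 (SAP 7.4, CLUE Comfort Scores); 112 completers per arm (SAP 7.4); Period 1 means and SDs as above; planned rule at one-sided 2.5% (SAP 10.1).

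**Method.** One-sided two-sample t test. Noncentrality = (difference + 5) / (SD × √(2/112)), with 222 degrees of freedom. Power is the noncentral-t probability above the critical value (1.652 at 5%, 1.971 at 2.5%).

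**Step 1: the plan's own figure.** With difference 2 and SD 21, noncentrality = 7 / (21 × 0.13363) = 2.494.
- One-sided 5%: 80.0%.
- One-sided 2.5%: 70.0%.

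Neither is 87%. At one-sided 5% with SD 21, about 87% returns if the historical 2.76 replaces the stated 2: noncentrality 7.76 / 2.806 = 2.765, power 86.7%. One-sided 10% with difference 2 gives 88.7%, but no text supports that level. A two-bound ±5 equivalence test gives under 10%.

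**Step 2: the SD.** With 112 per arm, Var(difference) = 21.066²/112 + 24.197²/112. The common SD giving the same variance is

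√((443.78 + 585.49)/2) = √514.64 = 22.69.

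Any weighted pooling of the two SDs is at least 21.066, so 21 cannot be a two-arm value.

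**Step 3: change only the SD** (noncentrality 2.309 for difference 2, and 2.560 for 2.76).

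| Difference | Level | SD 21 | SD 22.69 | Loss (points) |
|---|---|---|---|---|
| 2 | one-sided 5% | 80.0% | 74.4% | 5.6 |
| 2 | planned rule (2.5%) | 70.0% | 63.3% | 6.7 |
| 2.76 | one-sided 5% | 86.7% | 81.8% | 4.9 |
| 2.76 | planned rule (2.5%) | 78.6% | 72.2% | 6.4 |

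**Step 4: split the distance from 87% to 63%.** From 87% to 70.0% is 17.0 points, present with SD 21 unchanged (the assumed difference and the level). From 70.0% to 63.3% is 6.7 points, due to the SD.

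**Step 5: is 21 really the Test-arm value?** The documents do not say so. A second printed power points the same way. For CLUE overall quality of vision (Period 1 difference 64.49 - 64.44 = 0.05, one-sided 5%), the Test SD 17.221 gives 70.6%, against a printed 71%. The two-arm SD √((17.221² + 23.351²)/2) = 20.52 gives 57.6%. The handling figure of 63% does not return this way (36% with its Test SD and table difference), so nothing rests on it.

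**Step 6: baseline adjustment.** Residual SD = 22.69 × √(1 - r²). This equals 21 when r = √(1 - 441/514.64) = 0.378. The plan gives no r, so the values below are assumptions; difference 2.

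| r | Residual SD | One-sided 5% | Planned rule |
|---|---|---|---|
| 0.2 | 22.2 | 75.9% | 65.0% |
| 0.3 | 21.6 | 77.9% | 67.4% |
| 0.4 | 20.8 | 80.7% | 70.8% |
| 0.5 | 19.6 | 84.5% | 75.6% |

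**The case against.** **The source of 21 is inferred.** The documents also give a CLUE population SD of 20, and 21 exceeds it, so 21 could be read as a cautious planning value. That it is the Test-arm SD remains an inference. But the text cites Period 1, not the population figure, and Period 1 does not yield 21 for a two-arm comparison.

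**22.7 is itself uncertain.** Period 1 numbers per lens are not printed. If a common variance is assumed, the pooled SD depends on them: 22.2 at an assumed 2:1, or 21.9 at the 430:135 subject ratio of the slit lamp table. At 21.9 the loss for difference 2 is roughly 3 to 4 points. The precision of the Control SD is also unknown: with an assumed 50 Control subjects its 95% interval would be about 20.2 to 30.2. This stands as a caution about size. It does not support 21: every weighting lies above it, and if the arm SDs differ, a 1:1 trial weights them equally whatever the historical counts.

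**The analysis adjusts for baseline.** True, and with r of about 0.38 or more an SD of 21 would be adequate. The power lost through the SD might therefore be fully recovered. But the sizing text names an unadjusted test and states no correlation, so the plan does not make this argument.

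**Stronger readings to avoid.** A reader might infer that the SD explains the whole distance from 87% to 63%; Step 4 shows that it does not. A reader might take the 5 to 7 points to hold at any significance level; for difference 2 the loss is 7.3 points at one-sided 1%, 4.0 at 10% and 2.2 at 20%. A reader might also conclude that 112 per arm rests on SD 21, because difference 2, SD 21 and one-sided 5% need exactly 112 per arm for 80% power (131 with SD 22.69). The documents do not establish that: SAP 7.4 ties 224 to the slit lamp simulation and then names slit lamp and comfort jointly.

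**Conclusion.** The SD input is wrong as written. The value 21 is attributed to Period 1 but matches only the Test arm and is below any pooled value; the matching figure for a 1:1 comparison is about 22.7. At 112 per arm this lowers comfort power by about 5 to 7 points at one-sided 5% or 2.5%, the two levels the documents could support. On the planned rule, power before baseline adjustment is about 63% for a 2-point difference and about 72% for 2.76.

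These figures rest on the printed Period 1 SDs carrying over to this trial, equal allocation, 112 completers per arm and a t-test approximation to the Bayesian rule. That the printed 87% cannot be recovered from 2, 21 and -5 (80% or 70%) is a separate defect, and the larger one.

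**What to change.** In SAP 7.4 and Protocol 14.2, replace the SD of 21 with a common SD of 22.7, described as the root mean square of the Period 1 SDs 21.066 and 24.197. In SAP Table 11 and Protocol Table 12, restate comfort power at 224 completers on the planned decision rule: about 63% for a 2-point difference, or about 72% for 2.76. Say which difference is used, and that the figure is before baseline adjustment.

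If the sponsor wishes to credit the baseline covariate, print the assumed correlation r and its source, and use 22.7 × √(1 - r²).

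The cost is one sentence and one table cell in each document, and a less favourable stated power. No change to enrolment, procedures or the analysis model is asked for.
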